Wounds will be assessed postoperatively at regular intervals until wound healing is achieved. This will occur at least 2 and 6 weeks after surgery, which are standard intervals in our current postoperative protocol. No additional office visits will be needed for patients in the control or treatment arms. Photodocumentation of the wounds will occur at two and six weeks postoperatively. Primary outcome measure will be uneventful wound healing (requiring no intervention) versus the occurrence of wound complications (wound drainage, breakdown, necrosis, dehiscence, superficial or deep infection) requiring additional intervention. Intervention will be defined as any attempt of the surgeon to improve wound healing (in-office debridement, topical ointment, aspiration, antibiotic therapy, or return to the OR for the wound). Secondary outcome measures will include duration of wound healing delay, length of hospital stay, number of days of antibiotic therapy, and direct and estimated indirect costs. Statistical analysis will be performed to detect differences in the treatment groups

An *a priori* sample size calculation was performed based on data from our pilot study and from the existing literature. Currently, our retrospective data indicates wound complications should occur in approximately 31% of our "high risk" patients in the control group. We do not have reliable retrospective data for the study ciNPT group, so we are assuming a 4.57 relative risk reduction in wound complications using the ciNPT device based on existing data in the literature. An intention-to-treat analysis will be used. Given the short-term nature of this study, our expected dropout rate is very close to zero (and will in all likelihood be zero). Assuming an ITT analysis, any dropouts should be counted as failures. With an estimated dropout rate of 5%, the incidence of wound complications in the control group would be 34.5% and the incidence of wound complications in the ciNPT group would be 11.5%. Our assumptions include an equality analysis, 2-sided p-value < 0.05, and Fisher's exact test. Using these baseline assumptions, 116 patients (58 per group) will be required to achieve 80% power.

Based on our pilot study, 37% of our patient population should meet our inclusion criteria. Patients will need to be followed for at least 90 days to assess postoperative wound healing complications.

INCLUSION AND EXCLUSION CRITERIA Subject Selection

Version Date: 10/22/12 Page 3 of 6

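### Does a 90-day follow-up requirement with no dated assessment after week 6 leave the primary outcome undefined?

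*Combined protocol and SAP*

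**What the plan says.** All the relevant statements on timing are in the protocol's Experimental Design section.

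- **Follow-up:** "Patients will need to be followed for at least 90 days to assess postoperative wound healing complications".
- **Assessments:** "Wounds will be assessed postoperatively at regular intervals until wound healing is achieved". The next sentence dates them: "This will occur at least 2 and 6 weeks after surgery, which are standard intervals in our current postoperative protocol". The section adds "No additional office visits will be needed for patients in the control or treatment arms".
- **Photographs:** "Photodocumentation of the wounds will occur at two and six weeks postoperatively".
- **Endpoint:** "Primary outcome measure will be uneventful wound healing (requiring no intervention) versus the occurrence of wound complications" requiring additional intervention. Intervention means any step the surgeon takes to improve healing, from topical ointment to a return to the operating room. No time window is attached.
- **Dropouts:** "Given the short-term nature of this study, our expected dropout rate is very close to zero", and "Assuming an ITT analysis, any dropouts should be counted as failures". The sample size calculation nevertheless allows for 5%.

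Two other sections bear on the point. Informed Consent lets the researchers use data from the medical record. Discontinuation of Study/Subject Withdrawal lists missed study visits among the reasons for which an investigator may withdraw a subject, without giving a completion date.

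**The concern.** Week 6 is day 42. A patient whose wound is judged healed by then has no dated contact for days 43 to 90, which is 48 of the 90 days (53%). If that patient's record is silent afterwards, two scores seem possible: success, because the wound healed without intervention, or failure, because the patient was not followed to day 90 and dropouts count as failures.

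Patients and treating surgeons know the treatment arm, so one would not want this choice made after the data are in. The near-zero dropout expectation is also easier to meet at a routine week 6 visit than at day 90. If many silent patients were scored as failures, both event rates would rise, the risk ratio would move towards 1, and power would fall.

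**Working it through.** **1. The plan's own figure.** Inputs from Experimental Design: control rate 31%; an effect of 4.57, read as a ratio; 5% dropout counted as failure; two-sided Fisher's exact test at 0.05; 58 per group.

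- Control rate with dropout: 0.31 × 0.95 + 0.05 = 0.3445 (stated as 34.5%).
- ciNPT rate before dropout: 0.31 / 4.57 = 0.0678. With dropout: 0.0678 × 0.95 + 0.05 = 0.1144 (stated as 11.5%).
- Exact Fisher power, by full enumeration of two binomials at 0.345 and 0.115: 79.5% with 57 per group and 80.5% with 58. The stated 58 per group reproduces.

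**2. Do the timing statements conflict?** No. The visits at weeks 2 and 6 are introduced as a minimum, and 90 days is also a minimum. A wound unhealed at week 6 continues to be assessed under the until-healed rule. The full routine visit schedule is not in the documents, so a later routine visit cannot be excluded. What is missing is a named data source for wounds healed by week 6.

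**3. Which score does the text favour for a healed, silent patient?** A patient seen at weeks 2 and 6 has missed no dated visit, so the missed-visit ground for withdrawal does not apply to that patient. This makes the failure score the less natural reading, although the withdrawal section does not settle the matter.

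**4. How much could scoring matter?** The documents give no rate of loss after week 6, so both cases below are assumptions. They start from the pre-dropout rates of 31% and 6.78%, with 58 per group.

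*Case A: k healed but silent patients per arm are scored as failures.* Each rate becomes p + k/58.

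| k per arm | Control | ciNPT | Fisher power |
|---|---|---|---|
| 0 | 31.0% | 6.8% | 90.4% |
| 3 | 36.2% | 12.0% | 83.7% |
| 4 | 37.9% | 13.7% | 81.7% |
| 5 | 39.6% | 15.4% | 79.9% |

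Rounded to patients, 0.31 × 58 = 17.98 (18) and 0.0678 × 58 = 3.93 (4).

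| k per arm | Failures | Fisher p | Risk ratio |
|---|---|---|---|
| 0 | 18 vs 4 | 0.0016 | 4.5 |
| 3 | 21 vs 7 | 0.0043 | 3.0 |
| 6 | 24 vs 10 | 0.0075 | 2.4 |

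The risk difference is 14/58 = 24.1 points throughout, because equal counts are added to each arm.

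*Case B: an equal share x of all patients is lost and scored as failure.* Each rate becomes p(1 − x) + x.

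| x | Control | ciNPT | Difference | Fisher power |
|---|---|---|---|---|
| 0% | 31.0% | 6.8% | 24.2 points | 90.4% |
| 5% | 34.5% | 11.4% | 23.0 points | 80.6% |
| 5.3% | 34.7% | 11.7% | 22.9 points | 80.0% |
| 10% | 37.9% | 16.1% | 21.8 points | 70.6% |

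At x = 5.3% the extra failures number 0.053 × 0.69 × 58 = 2.1 in control and 0.053 × 0.932 × 58 = 2.9 in ciNPT. Power crosses 80% near 5% because the trial was sized for 80% at 5% dropout. That 5% is the plan's margin over its near-zero expectation.

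**The case for a change.** The strongest case for a change is that a 90-day minimum is not a method of ascertainment. Permission to read the record is not a planned review. A silent record cannot separate an event-free patient from one treated elsewhere. Deep infection and return to the operating room are part of the endpoint, reoperation is a stated aim, and the protocol itself says 90 days are needed. In an open-label trial the scoring rule is better written down in advance. Doing so would take a few sentences, a record check or call for each of 116 patients, and an IRB modification.

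Much of this stands. The window, the data source and the dropout date are not stated together anywhere, and the reported rates and risk ratio would depend on the scoring rule if silent records were common. What does not follow is that the plan as written leads to a wrong result. The 90-day sentence states its purpose as assessing wound complications, so it supplies the window in substance. The endpoint is built from surgeon actions that are normally charted. Nothing in the documents suggests that silent records would be frequent or would differ between arms.

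**Conclusion.** The gap is real but does not call for a change. A competent team would fill it sensibly: the outcome runs from surgery to day 90, events are read from visits and the medical record in the same way in both arms, and a dropout is a patient whose wound status at day 90 is unknown. This rests on the 90-day sentence being read as the outcome window and on interventions being charted.

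The sample size stands at 58 per group (80.5% power). In the illustrations, power stays above 80% with up to 4 healed but silent patients per arm scored as failures, or with an equal share lost of up to about 5.3%. In the equal-count examples (k = 0, 3 and 6) every p-value is below 0.01. The actual amount of loss after week 6 cannot be derived from the documents, so these are ranges under assumption and not estimates. Arm-dependent scoring was not modelled, and the documents give no evidence of it.

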NCT03061903

STUDY TITLE

Closed Incision Negative Pressure Therapy vs. Standard of Care for Surgical Incision Management in High-Risk Patients following Total Hip Arthroplasty: A Randomized Controlled Trial

DOCUMENT DATE: 10/22/2012

Version Date: Page 1 of 6

RESEARCH PROTOCOL

STUDY TITLE

Closed Incision Negative Pressure Therapy vs. Standard of Care for Surgical Incision Management in High-Risk Patients following Total Hip Arthroplasty: A Randomized Controlled Trial

Investigators

[name], Assistant Professor of Orthopedic Surgery (Principal Investigator)

Study Coordinator

[name]
[contact]
[contact]

Lead Institution

Center for Hip & Knee Replacement Department of Orthopaedic Surgery Columbia University Medical Center [contact]

INTRODUCTION

Direct anterior approach (DAA) for total hip arthroplasty (THA) is becoming increasingly popular, with an estimated 25% of all procedures being performed through this approach in the United States. However complications have been reported such as an increased risk of wound complications and surgical site infections. Jewett et al¹ cited having a 4.6% wound complication rate with this approach. Christensen et al² also reported 1.4% of their direct anterior approach total hips replacements required reoperation for wound complications versus 0.2% of their posterior approach hips. Using stricter criteria to define wound complications, we have recently published a retrospective analysis of 651 consecutive DAA hips,³ identifying an 11.5% wound complication rate and a 1.9% reoperation rate for these wound complications.

Risk factors for surgical site infections and prosthetic joint infections have been studied in the arthroplasty population. Many have been identified and include morbid obesity and increased comorbidities such as diabetes. ^{4,5,6} In our retrospective study,³ we have specifically identified BMI > 30 kg/m², the presence of diabetes, active smoking status, and previous hip surgery as risk factors for wound complications and reoperation. Based on preliminary data, we documented a 31% wound complication rate in this "high-risk" subset of patients using standard-of-care dressings and incision management. This rate is unacceptably high for a common elective operation, prompting the desire to investigate alternative therapies.

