The goal of this study is to determine the efficacy of ciNPT for prevention of wound complications and return to the operating room for wound complications in patients with pre-determined risk factors that affect wound healing (BMI > 30kg/m², diabetes mellitus, smoking, history of prior hip surgery). This is will be a prospective, randomized, controlled trial. Inclusion criteria will be patients undergoing DAA THA by the investigating surgeons that have at least one risk factor for complicated wound healing as described above, based on previous retrospective data. Subjects will be randomly assigned to either the ciNPT intervention group or the control group using computer-generated, randomized envelopes with equal numbers in each treatment arm. Both dressings will be applied under sterile conditions at the end of the DAA THA surgery, while still in the operating room, and then removed after 7 days.

Patients randomized to the control group will receive a conformable, water resistant, silver-impregnated, antimicrobial hydrofiber dressing (AQUACEL® Ag, Convatec) which is currently the standard of care at our institution for postoperative wound dressing. This dressing is left in place for 7 days and then removed by the patient or visiting nurse at home. Patients randomized to the study group will receive an incisional ciNPT device, which is currently being used selectively in high-risk patients at our institution (Prevena™, KCI). Both wound dressings are FDA-approved devices. Due to the obvious difference in appearance of the two dressings, neither patients nor treating surgeons can be blinded to treatment arm.

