Prospective inclusion criteria:

- 1. Patients undergoing primary THA through a direct anterior approach by one of the investigating surgeons
- 2. The presence of one or more of these risk factors for delayed or problematic wound healing:
 - a. Diabetes
 - b. Obesity (BMI > 30)
 - c. Active smoking
 - d. Previous Hip Surgery

RECRUITMENT PROCEDURES

Patients will be recruited in the offices of the treating surgeon if they meet subject criteria, based on routine consultation. No active recruitment, such as advertisements, will be made. No compensation will be offered to participants.

DATA COLLECTION

Columbia University Medical Center will be used as a central location for data processing and management. Vanderbilt University, with collaboration from a consortium of institutional partners, has developed a software toolset and workflow methodology for electronic collection and management of research and clinical trial data. REDCap (Research Electronic Data Capture) data collection projects rely on a thorough study-specific data dictionary defined in an iterative self-documenting process by all members of the research team with planning assistance from the Biostatistics Unit of Columbia University Medical Center. The iterative development and testing process results in a well-planned data collection strategy for individual studies. REDCap servers are housed in a local data center at Columbia and all web-based information transmission is encrypted. REDCap has been disseminated for use locally at other institutions and currently supports 965 active institutional partners and other institutions in 78 countries (www.project-redcap.org).

INFORMED CONSENT

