If subject wish to be withdrawn from the study at anytime, then they may do so and contact the surgeon investigators with this request. Subjects may also be withdrawn by the investigators for the follow reasons:

- failure to follow instructions,
- failure to show up for study visits,
- it is not in the subject's best interest to continue on this study, or
- the study is stopped.

ADVERSE EVENTS

Adverse events occurring as a result of experimental intervention is not anticipated. However, if such event does arise, this will be documented and written report will be given to the IRB and sponsor.

DATA AND SAFETY MONITORING

The Principal Investigator will be tasked with ensuring the safety of the study. The Principal Investigator will review the aggregate data every 6 months to determine if aspects of the study need to be changed or stopped. In addition, the Principal Investigator will review any and all deviations, adverse events and unanticipated problems that may occur to determine their relatedness to the study, their severity, and whether they require study changes. In addition, any unanticipated problems or instances of non-compliance will be reported to the IRB as per their reporting requirements. If any protocol changes are needed, the investigator will submit a modification request to the IRB. Protocol changes will not be implemented prior to IRB approval unless necessary to eliminate apparent immediate hazards to the research subjects. In such a case, the IRB will be promptly informed of the change following implementation.

CRITERIA FOR EVALUATING RESPONSE/STATISTICAL ANALYSIS

For the randomized control trial, a t-test for independent samples or a nonparametric Mann-Whitney U test will be used for determination of differences of mean values between the two treatment groups. The Kolmogorov-Smirnov test will determine the distribution form. For analysis of categorical data, a Fisher exact test will be used. The level of alpha will be set at p < 0.05.

REFERENCES/BIBIOGRAPHY

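### The four risk factors that define eligibility are used in neither the allocation nor the primary analysis; stratifying the analysis by number of factors would recover some precision at almost no cost

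*Combined protocol and SAP*

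**What the plan says.** The eligibility list requires a primary direct anterior hip replacement and "The presence of one or more of these risk factors for delayed or problematic wound healing": diabetes, BMI above 30, active smoking or previous hip surgery. Any one suffices, so the trial will contain patients with one to four factors. Surgery is by "Patients undergoing primary THA through a direct anterior approach by one of the investigating surgeons" in the sense of the first criterion, which implies more than one surgeon; the number is not given.

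The Introduction reports that the investigators' retrospective series identified BMI above 30 together with "the presence of diabetes, active smoking status, and previous hip surgery as risk factors for wound complications and reoperation". It gives no rate or odds ratio for any single factor, and none by number of factors.

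The Experimental Design section allocates patients "using computer-generated, randomized envelopes with equal numbers in each treatment arm". No strata, blocks or minimisation factors are named.

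The statistical analysis section, on binary outcomes, says: "For analysis of categorical data, a Fisher exact test will be used". No stratified test, covariate-adjusted model or sensitivity analysis by risk factor or surgeon appears anywhere. The sample size rests on the same test: "Our assumptions include an equality analysis, 2-sided p-value < 0.05, and Fisher's exact test".

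**The concern.** The plan selects patients on characteristics it believes drive the outcome, then makes no further use of them. An obese patient with no other factor and an obese diabetic smoker with prior hip surgery count alike. With 58 per arm, the share of multi-factor patients can differ between arms by chance, and nothing in the plan prevents or corrects this.

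Two things are at stake. One is precision: part of the outcome variation may be explained by data held at entry, and a crude test leaves it as noise. The other is how a single result near the significance threshold will be read. If the baseline table shows an imbalance and no adjustment was prespecified, any later adjustment will look chosen after the fact.

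**Working it through.** **1. The plan's own figure.** The control rate is 31%, the assumed reduction is 4.57-fold (31%/4.57 = 6.8%), and 5% dropouts count as failures:
- control: 0.95 × 31% + 5% = 34.45%, stated as 34.5%
- ciNPT: 0.95 × 6.78% + 5% = 11.44%, stated as 11.5%

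Full enumeration of the two-sided Fisher test at 34.5% versus 11.5% gives 79.5% power with 57 per group and 80.5% with 58. The stated 58 per group reproduces. Expected events are 0.345 × 58 = 20 and 0.115 × 58 = 6.7, about 27 in total.

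**2. Validity of the planned test.** In simulations with a binary prognostic stratum and no device effect, the unadjusted Fisher test under simple 58:58 allocation rejected in about 3% of trials.

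**3. How often the arms are unbalanced.** Assume 40% of patients have two or more factors (not in the documents).
- The SD of the between-arm difference in that share is √(0.4 × 0.6 × 2/58) = 0.091, so the 95% range is about ±18 points.
- With independent binomial draws, a difference of at least 10 points occurs in 30% of trials and at least 15 points in 11%.
- With the total fixed at 46 of 116 (hypergeometric), the figures are 34% and 9%.

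**4. What a 15-point imbalance does.** Take two assumed pairs of control risks (one factor; two or more), both averaging 31%:
- 0.6 × 18% + 0.4 × 50.5% = 31%
- 0.6 × 23% + 0.4 × 43% = 31%

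Fifteen points between arms means each arm sits about 7.5 points from the common share.

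| | 18% / 50.5% | 23% / 43% |
|---|---|---|
| Shift in control rate | 0.075 × 32.5 = 2.4 points | 0.075 × 20 = 1.5 points |
| Opposite shift in ciNPT rate, planned effect | 2.4/4.57 = 0.5 | 1.5/4.57 = 0.3 |
| Shift in difference, planned effect | about 3.0 | about 1.8 |
| Shift in difference, no device effect | 0.15 × 32.5 = 4.9 | 0.15 × 20 = 3.0 |

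Counting 5% dropouts as failures would shrink each entry by the factor 0.95. For scale, the planned difference is 34.5 − 11.5 = 23 points, and its standard error is √(0.345 × 0.655/58 + 0.115 × 0.885/58) = 7.5 points.

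**5. Where it could matter.** Shifts of this size are worth an event or two per arm (3.0% of 58 = 1.7). At the planned result, 20 versus 7 gives Fisher p = 0.008, so that is no threat. Near the threshold one event decides: 20 versus 9 gives p = 0.031 and 20 versus 10 gives p = 0.055.

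**6. What stratifying the analysis gains.** Simulated at N = 116 with the existing allocation and the risks in step 4, power is about 80% for Fisher, 82–83% for an exact stratified test and 86% for Mantel-Haenszel, each with type I error at or below about 5%. Much of the Mantel-Haenszel gain over Fisher comes from dropping Fisher's conservatism. In simulations assuming a high-risk stratum of 30–50% with odds ratio 2–4, an unadjusted chi-square test already has about 85–86%, and stratified allocation plus Mantel-Haenszel has about 86–89%. The gain from using the risk factor itself is therefore up to a few points.

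**The case against.** The strongest reply is that randomisation already accounts for chance imbalance: its contribution to variation is inside the Fisher test's error rate. That stands. Even with a 15-point imbalance fixed in place (28 versus 19 of 58 patients with two or more factors) and no device effect, the simulated false-positive rate was about 5% for the 18%/50.5% risks and about 4% for 23%/43%. Conditional power with that imbalance falls from 81% to 69% or 74% if it is adverse, and rises to 90% or 87% if favourable. Averaged over allocations, the planned power holds.

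A reader might therefore go too far by inferring that a positive result could not be told apart from case mix. The documents do not support that: allocation is random, the test holds its level, and the planned effect is large beside the shifts above. A reader might also take the 15-point imbalance as moving the control rate itself by 4.9 points. That figure is the shift in the difference between arms, and only if the device does nothing.

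It is also fair to say that the inputs are assumed. The documents give no share with two or more factors and no risk gradient within the eligible population. Their overall figures (37% eligible, 31% complications among them, 11.5% overall) are consistent with strong factors, since 0.37 × 31% = 11.5%, provided they describe comparable populations. But that contrasts some factor with none, not one factor with several.

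Finally, surgeon looks like an equally natural stratum, because the primary outcome depends on an unblinded surgeon's decision to intervene. Its effect cannot be sized, since neither the number of surgeons nor their rates are given. Surgeon-specific blocks in an open-label trial would also make the next allocation easier to predict. That objection stands against making surgeon a required stratum.

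**Conclusion.** The point holds as a matter of precision and chance imbalance. The plan enriches on four named predictors and uses none of them in allocation or in the primary test. It is not an error: the Fisher test is valid and the sample size is correctly calculated. Nor is it a source of systematic bias.

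Its size is modest. On the assumed 40% share and the two assumed risk pairs, about one trial in ten would have a 15-point imbalance, worth 3.0 or 1.8 points of treatment difference under the planned effect. That would rarely reverse the planned result but could decide a borderline one. No claim about the size of a surgeon effect can be made from the documents. The change is worth making because it is cheap and has credibility only if specified before outcomes are seen.

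**What to change.** In the statistical analysis section, prespecify the primary comparison as a test stratified by number of risk factors (one versus two or more), and report a stratum-adjusted risk difference with its confidence interval. Choose either the exact stratified test or Mantel-Haenszel now and name it. Keep the unadjusted Fisher test as a sensitivity analysis. Use the single two-level factor only: with about 27 expected events, separate terms for all four factors plus surgeon would be too many. N stays at 116.

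If the envelopes have not been made, also stratify the list by the same two-level factor, with randomly varying block sizes. If they exist, keep the allocation and change only the analysis.

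Treat surgeon as optional, in a sensitivity analysis with low-volume surgeons pooled.

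The cost is a few lines of analysis text and, if the list is stratified, a second envelope set. No new measurement is needed, provided all four factors are recorded for every patient and not only the one that qualified them. The change should be fixed without sight of outcomes by arm, which matters because the principal investigator reviews aggregate data every six months.

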Patients willing to participate in the prospective study will be given written informed consent preoperatively. This will be performed by one of the investigators. Subjects will be informed that this study is being done to evaluate the potential effects of closed incision negative pressure therapy (ciNPT) on reduction of overall wound complications following direct anterior approach (DAA) total hip arthroplasty (THA) in high-risk patients compared to the standard dry dressing. Participating allows the researcher to use data from his/her medical record. No identifying information will be transmitted to other parties. Benefits and risks of participation will also be explained. Patients will also be given the option not to participate and receive routine care. Tests and treatment given will be a part of the standard of care and no extra procedures or treatments will be required for solely research purpose.

DISCOMFORTS AND RISKS

The Prevena Incision Dressing has an acrylic adhesive coating and a skin interface layer with silver, which may present a risk of an adverse reaction (redness, rash, itching, swelling or bruising) in patients who are allergic or hypersensitive to acrylic adhesives or silver. These risks are essentially identical to those seen with the control dressing. Please note that there is no evidence to support the risk of adverse skin reaction will be any higher than that of a traditional postoperative dressing. No additional risks to the standard care are anticipated for this study.

POTENTIAL BENEFITS

This includes improved wound healing from the use of the negative pressure dressing. The goal of this study is to determine if there is advantage of using this dressing on a routine basis compared to the standard dressing.

DEVICE PRECAUTIONS

Participants should contact the investigator in the event of visual or audible alerts as this may signal a leak, full canister, low battery, or device error. Participants need to remove the Prevena device prior to having a magnetic resonance imaging procedure or other diagnostic imaging procedures. The device should not be worn during hyperbaric oxygen therapy. Contact with the device must be avoided in the event of defibrillation or electrocardiograms.

DISCONTINUATION OF STUDY/SUBJECT WITHDRAWAL

Version Date: 10/22/12 Page 4 of 6

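### The protocol flags silver and acrylic-adhesive allergy as a risk but has no eligibility rule for it, although both dressings contain silver and the consent description misdescribes the control dressing

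*Combined protocol and SAP*

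**What the plan says.** All references are to the combined protocol and SAP.

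- **Discomforts and Risks.** "The Prevena Incision Dressing has an acrylic adhesive coating and a skin interface layer with silver", and this may cause a skin reaction "in patients who are allergic or hypersensitive to acrylic adhesives or silver". On the comparison between arms it adds: "These risks are essentially identical to those seen with the control dressing".
- **Experimental Design.** The control is a "water resistant, silver-impregnated, antimicrobial hydrofiber dressing", described as the institution's current standard. Either dressing is put on in the operating room and stays on for 7 days. Allocation is by envelope, with equal arms.
- **Eligibility.** The heading reads "INCLUSION AND EXCLUSION CRITERIA Subject Selection". Beneath it stands one list, "Prospective inclusion criteria", with two items: primary THA by the direct anterior approach under an investigating surgeon, and at least one of four wound-healing risk factors. Recruitment Procedures follows directly.
- **Informed Consent.** Subjects are to be told that ciNPT is being studied "in high-risk patients compared to the standard dry dressing". The same section says that risks and benefits will be explained and that patients may decline and have routine care.
- **Discontinuation of Study/Subject Withdrawal.** An investigator may withdraw a subject whose interests are not served by continuing.

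**The concern.** The protocol identifies a group of patients who may react to the dressing materials, but its eligibility section does not say what to do with them. The heading promises exclusion criteria and none is given. There is no redaction mark or visible gap that would explain their absence. An obese patient with a documented silver allergy meets both inclusion items.

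Silver matters most because neither arm avoids it. Where only one arm carries a hazard, the question is one of allocation. Here the stated rules lead to the flagged exposure whichever envelope is opened.

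The consent wording compounds the gap. A subject who knows of a silver allergy could raise it if told what each dressing contains, but the phrase used for the comparator gives no hint of silver. At stake are the protection of a small group that the protocol itself names, and agreement between three of its sections.

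**Working it through.** **Background check of the plan's own figure.** The point does not depend on the sample size, but the figure was checked.

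- Inputs from Experimental Design: control rate 31%; a 4.57-fold reduction; 5% dropout counted as failure; two-sided Fisher's exact test at 0.05; 58 per group for 80% power.
- Control rate with dropouts as failures: 0.31 × 0.95 + 0.05 = 0.3445, stated as 34.5%.
- ciNPT rate: 31% / 4.57 = 6.8%; then 0.068 × 0.95 + 0.05 = 0.1146, stated as 11.5%.
- Exact Fisher power at 34.5% against 11.5%, by enumerating the two binomial distributions: 79.5% with 57 per group and 80.5% with 58. The stated 58 per group reproduces, and nothing below changes it.

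**The sections side by side.**

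1. *Is the group identified?* Yes. Discomforts and Risks names allergy or hypersensitivity to either material.
2. *Is the group kept out or screened?* No. The eligibility section has two inclusion items and no exclusion. Recruitment Procedures takes patients who meet those criteria and mentions no allergy history. No other section supplies the rule.
3. *Which arm contains which material?*

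| Material | ciNPT dressing | Control dressing | Documented chance of exposure once randomised |
|---|---|---|---|
| Silver | Yes (Discomforts and Risks) | Yes (Experimental Design) | 0.5 + 0.5 = 100% |
| Acrylic adhesive | Yes (Discomforts and Risks) | Not described | at least 0.5 = 50% |

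4. *Does the consent description match the design?* No. Experimental Design gives a water-resistant hydrofiber dressing containing silver. Informed Consent gives a dry dressing and does not mention silver in the control arm.
5. *Does the withdrawal provision fill the gap?* Not fully. It acts after enrolment, and the sample-size text in Experimental Design says that dropouts count as failures. It cannot replace a rule applied before randomisation.
6. *How many patients?* This cannot be calculated, because the documents give no prevalence of either allergy.

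**The case against.** The best defence is that clinical judgement already covers this. Patients are recruited by the treating surgeon at a routine consultation, risks are to be explained, patients may decline, and investigators may withdraw a subject. That stands as partial mitigation. None of it makes a known-allergic patient ineligible or requires anyone to ask about allergy before the envelope is opened.

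A reader might infer four stronger conclusions, which the documents do not support.

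- *An acrylic-allergic patient is exposed in both arms.* The control adhesive is not described. The statement that risks are essentially identical does not establish that acrylic is present.
- *The consent process conceals the control-arm exposure.* The protocol says that risks will be explained, and its own risk text says that the control dressing carries much the same risks. The consent form is not available for review. What is shown is a misdescription of the comparator.
- *Randomisation adds exposure to silver.* The silver control is the institution's standard dressing, so silver is the default outside the trial too. How known-allergic patients are handled in routine care is not stated, so added exposure is not demonstrated.
- *The primary outcome is biased.* The reactions named (bruising, itching, rash, redness and swelling) are not among the wound complications in the primary definition, which also requires an intervention aimed at wound healing. A reaction that progressed to drainage or breakdown could count, but nothing in the documents says how often that would happen. For silver, both arms are exposed and no difference between them is shown. One event in 58 is 1.7 percentage points (1/58), but that is true of any event and does not measure this problem.

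**Conclusion.** The point holds as a gap in eligibility and a mismatch in the consent description. Under the stated rules a patient with a known silver allergy is eligible and receives a silver-containing dressing with certainty. For known acrylic-adhesive allergy the documented chance is at least one half. The conclusion assumes that the eligibility list is complete as published and that no separate screening form adds an allergy rule.

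The number of patients affected is unknown and, as a matter of judgement, probably small. No effect on the primary outcome, the power or the 58 per group is shown. The correction is worth making because the protocol itself raises the risk and the remedy is cheap. Confidence is high in the textual gap, but does not extend to consequences beyond it.

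**What to change.** 1. Reconcile the eligibility section with Discomforts and Risks. State whether patients with known hypersensitivity to silver or acrylic adhesive are eligible, and have this settled before randomisation, for example by an allergy question on the eligibility form. The rule itself is for the investigators to set.
2. In Informed Consent, replace the dry-dressing phrase with the description of the control dressing in Experimental Design, so that subjects are told that both dressings contain silver.
3. State whether the control dressing contains acrylic adhesive, so that the statement of near-identical risks can be checked.

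The cost is a sentence in the eligibility section, one form item and minor wording changes. If the investigators decide against eligibility, a few otherwise eligible patients may be lost. The sample-size calculation need not be redone.
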